#### III. Treatment

#### A. Patient selection

The use of human subjects in this project will be submitted for approval by the Institutional Review Board (IRB) at the University of Michigan prior to conducting the study. Patients requiring an implant to replace a missing tooth in the premolar or 1st molar area will be recruited for this prospective controlled trial. A total of up to 40 subjects will be recruited with the goal of enrolling a minimum of 28 subjects divided into 2 groups (14 in each group) based upon the mucosa thickness (<2 mm and ≥2 mm). A prospective design will be applied and implants with a polished collar will be placed.\*

-

\* Biohorizons Tapered Internal Implant, Laser-Lok, RBT

Potential patients will be carefully screened according to the inclusion and exclusion criteria as

#### follows:

## **Inclusion Criteria**

- Male or Female
- Aged ≥18
- In need of one dental implant in the Maxillary or Mandibular area, premolar, or 1st molar tooth
- Natural adjacent teeth
- Bone height of ≥10mm
- Bone width of ≥5mm
- Good oral hygiene
- Stable periodontium
- Willingness to fulfill all study requirements

## **Exclusion Criteria**

- Need bone augmentation
- Need one dental implant that is anterior, a 2nd or 3rd molar tooth
- Current smoker or quit smoking less than one year
- Pregnant or plan to get pregnant
- Uncontrolled diabetes (HbA1C > 7)
- Medical conditions that may influence the outcome of the study (neurologic or psychiatric disorders, systemic infections )
- Current use of oral bisphosphonates
- History of IV bisphosphonates
- History of radiation therapy in the head and neck area within 4 years
- Poor oral hygiene (plaque score more than 40% based on O'Leary plaque score)
- Once a group has been filled, subjects who meet the criteria of that group will be excluded

#### **B.** Clinical assessments

Clinical measurements (probing depth, clinical attachment level and bleeding on probing) will be recorded using a UNC (University of North Carolina) manual probe. These measurements will be taken at two weeks post-operatory (V4), one month post-operatory (V5), crown impression (V6), crown restoration (V7), 6 months (V8), and 12 months (V9) after crown restoration. A tension-free caliper will be used to measure mucosa thickness at the time of surgery. Clinical photographs will be taken at each appointment as well as standardized radiographs. In addition, bone sounding procedure under local anesthesia will be performed on the mid buccal and lingual side of the implant sites at 12 month follow-up to assess the level of the underlying bone. Subjects will also be receiving a cleaning at no charge to them at their 6 and 12 month visits.

#### C. Radiographic assessment

Intraoral radiographs will be taken using a paralleling technique with a Rinn-type film holder at the initial appointment (V1), implant placement (V3), Crown impression (V6), crown delivery (V7), and at 6 (V8) and 12 (V9) months after crown restoration. The CBCT scan will be taken at the pre-implant surgery visit (V2) and the 12 month follow up (V9). Custom-made stents will be fabricated to ensure reproducibility and standardized radiographs. All assessments will be made by one examiner. Intra-examiner calibration will be performed.

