## **General Investigational Plan**

A single center, prospective controlled clinical trial is planned to investigate the effect of mucosa tissue thickness upon implant marginal bone changes on implant with smooth collar. Twenty eight adult patients who fulfill the inclusion criteria will be divided into 2 groups based upon the mucosa thickness (<2 mm and ≥2 mm). A signed written informed consent will be obtained from all subjects. Subjects will not be screened or treated until an informed consent has been obtained. Patient information will be protected according to the privacy regulations of the federal Health Insurance Portability and Accountability Act of 1996 (HIPAA).

The enrolled patients will receive implants with polished collar. Implants will be restored at 4 (±1) months after placement. Outcome analyses will be performed until 1 (±1 month) year after loading and clinical and radiographic parameters will be evaluated to compare clinical outcomes between groups. The primary outcome is implant marginal bone loss and probing depth from clinical and radiographic measurements.

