## **Study Protocol**

#### I. Introduction

The thickness of the gingiva (i.e. gingival biotype) varies between subjects. In 1969, Ochsenbein and Ross proposed two main types of gingival biotype ("pronounced scalloped" and "flat") and their relationship with the contour of the osseous crest. Subjects belong to pronounced scalloped biotype have thinner soft buccal tissues and more advanced soft tissue recession than subjects who had the flat biotype. Claffey & Shanley (1986) defined thin tissue biotype as a gingival thickness < 1.5 mm and thick tissue biotype as tissue having thickness ≥ 2 mm.

Several pre-clinical studies have examined how mucosal thickness affects marginal bone loss around implants. Abrahamsson et al. (1996) showed that sites with thin mucosa had an angulated pattern bone defects, whereas sites with an even pattern of the alveolar crest, the adjacent mucosa was consistently thick. Another study by Berglundh and Lindhe (1996) suggested that certain width of the peri-implant mucosa is required to protect osseointegration.

They showed when ridge mucosa was thin ( $\leq 2$  mm), more bone resorption and angular bony defect were noted.

A human prospective clinical trial reported that tissue/mucosa thickness may affect crestal bone stability around implants. Implants with a thick tissue biotype (>2 mm) had significantly less bone loss when compared to implants with thin tissue thickness (≤2 mm). Implants with initially thin tissue had bone loss up to 1.45 mm that occurred within the first year of function. Whereas thick tissues only had 0.2 mm bone loss that was noted. It was observed that thick mucosa formed an epithelial – connective tissue attachment to the titanium surface that protected and preserved the osseointegration. If this soft tissue dimension is not achieved, bone resorption might occur to establish a biological width of the epithelial – connective tissue attachment. Thus, it is suggested that a certain minimum width of peri-implant mucosa is required.

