## D. Surgical protocol

Preliminary alginate impressions will be taken at the screening appointment for the purpose of making study models to then be able to fabricate a reference stent and surgical guide. On the

implant surgery visitvital signs will be taken. Local anesthesia will be performed by using local infiltration technique with 2% Lidocaine with 1:100k epinephrine or 1:50k epinephrine. Intrasulcular and crestal incision design will be made along the crest of the ridge, bisecting the existing zone of keratinized mucosa. Full-thickness flaps are raised on the buccal and lingual/palatal side up to or slightly beyond the level of the mucogingival junction, exposing the alveolar ridge of the implant surgical sites. Once the flaps are reflected and the bone is prepared, a surgical guide will be inserted and a series of drills are used to prepare the osteotomy site incrementally. All implants will be placed according to the manufacturer's protocol (Biohorizons Tapered Internal Implant, Laser-Lok, RBT) and the rough-smooth junction will be placed to the bone crest. The buccal mucosal thickness will be measured at different levels. Implants with 9-13 mm length and 3-5 mm width will be used. After implant placement a healing abutment will be connected and interrupted sutures will be placed to close the flaps. After suturing, standardized radiographs will be obtained. Other radiographs will be taken during the surgery to check implant angulation, these will not be standardized. The surgery is being done as part of standard of care. Subjects will be instructed to rinse with warm salt water once a day every day for two weeks. All subjects will be prescribed 500mg of amoxicillin to take 3 times a day for ten days. If the subject is allergic to Amoxicillin, they will be prescribed 250 mg of Zithromax 6 tablets total /sig. 2 tablets the 1st day and Q.D. (1 x per day) until gone. In addition, the subject will be prescribed 600 mg of ibuprofen, taken as needed, for pain control. The sutures will be removed in 2 weeks.

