# IV. Outcome analysis

The measurement variables and correspondent measurement time points are summarized in the Table.

Measurement time	Measurements						
Clinical outcomes							
Baseline (V3)	Mucosa thickness						
At two weeks post-operatory (V4), one month post-operatory (V5), crown impression (V6), and at crown delivery (V7),	Probing depth, bleeding on probing, clinical attachment level						
6 (V8) and 12m (V9) after crown placement	Probing depth, bleeding on probing, clinical attachment level						
Radiographic outcome							
	Marginal bone level						
At screening (V1), implant/surgery baseline (V3), crown impression (V6), crown delivery (V7), 6m (V8), and 12m (V9) after crown placement.							

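### Nothing in the available plan keeps the single radiographic examiner unaware of thickness group, so a group-dependent reading of bone-level change, a primary outcome, is possible and unguarded; coded film reading would reduce the risk.

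*Combined protocol and SAP*

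**What the plan says.** The General Investigational Plan names the endpoint: "The primary outcome is implant marginal bone loss and probing depth from clinical and radiographic measurements". Section III.C, on radiographic assessment, assigns the reading: "All assessments will be made by one examiner. Intra-examiner calibration will be performed". That sentence stands under the radiographic heading, so it covers at least the films. The same section provides for custom stents and a paralleling technique.

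Thickness defines the groups, which are not randomised. Section III.B says "A tension-free caliper will be used to measure mucosa thickness at the time of surgery", and section III.D adds "The buccal mucosal thickness will be measured at different levels". Neither section names the person who measures. Group membership is also followed during recruitment, because the exclusion criteria state "Once a group has been filled, subjects who meet the criteria of that group will be excluded".

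Section IV lists marginal bone level as the radiographic outcome, at these times: "At screening (V1), implant/surgery baseline (V3), crown impression (V6), crown delivery (V7), 6m (V8), and 12m (V9) after crown placement". It does not define a change score or an interval.

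The available text does not mention blinding, masking, coded films or an independent reader. The front pages and the flow chart were not available, so this absence is established only for the rest of the document.

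**The concern.** Bone-level reading involves judgement, and the plan puts it in one person's hands. Stents limit projection error, and intra-examiner calibration limits inconsistency. A reader can be fully repeatable and still read thin-tissue sites differently from thick-tissue sites. With only one reader, no second reading would reveal it.

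The Introduction gives a reader an expected direction. It reports that, in an earlier human trial, implants in thick tissue "had significantly less bone loss when compared to implants with thin tissue thickness", with losses of up to 1.45 mm in thin tissue against 0.2 mm in thick. The Introduction also says that the question is still undetermined for smooth collars, so the expectation is not a settled result.

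A reading error that is the same in both groups cancels in the comparison. A group-dependent error also cancels if it is equal at baseline and follow-up. A group-dependent error in the change between films does not cancel. It passes in full into the estimated difference, and a larger sample does not remove it.

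**Working it through.** **Inputs from section V, Sample size:** two-sided 5% level, 80% power, difference 1.280 mm, SD 1.160 mm, 14 per group.

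**Assumptions:** bone loss is the change from V3 to V9, the SD applies to that change, and the true group difference is zero. The size of any reader shift is also assumed, because the documents give none.

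**Step 1: reproduce the plan's figure.** For a two-sample t-test with a difference of 1.28 mm and SD 1.16 mm, exact power is 0.770 with 13 per group and 0.802 with 14. The stated 14 per group is reproduced.

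**Step 2: standard error and significance threshold.**
- SE = SD × √(2/n) = 1.16 × √(2/14) = 0.438 mm, with 26 degrees of freedom.
- The smallest observed difference that reaches significance is 0.901 mm.

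**Step 3: effect of a reader shift.** Let b be the differential shift in change, thin minus thick. With no true effect, the test statistic follows a noncentral t distribution with 26 degrees of freedom and noncentrality b/SE. The false-positive rate is the probability that it falls beyond either critical value.

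| Shift b (mm) | b / 1.28 | b / SE | Two-sided rate | Tail showing more loss in thin tissue |
|---|---|---|---|---|
| 0 | 0% | 0 | 5.0% | 2.5% |
| 0.1 | 8% | 0.23 | 5.6% | 4.1% |
| 0.2 | 16% | 0.46 | 7.2% | 6.4% |
| 0.3 | 23% | 0.68 | 10.1% | 9.7% |
| 0.5 | 39% | 1.14 | 19.6% | 19.5% |

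A simulation of 200,000 runs gave 5.5%, 7.1%, 10.1% and 19.6% for the four non-zero shifts.

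**Step 4: cancellation.** The shift in change is the shift at V9 minus the shift at V3. Take 0.3 mm at V9:
- V3 shift 0: 0.3 − 0 = 0.3 mm, rate 10.1%.
- V3 shift 0.15 mm: 0.3 − 0.15 = 0.15 mm, rate 6.3%.
- V3 shift 0.3 mm: 0.3 − 0.3 = 0, rate 5.0%.

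**Step 5: dependence on the SD.** The rate reaches 10% at b = 0.297 mm when the SD is 1.16 mm. The rate depends on b only through b/SD, so the doubling point scales with the SD:
- Assumed SD 0.8 mm: 0.297 × 0.8/1.16 = 0.20 mm.
- Assumed SD 0.5 mm: 0.297 × 0.5/1.16 = 0.13 mm.

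**Step 6: effect on power.** If the true difference were 1.28 mm, a 0.2 mm shift would move power from 0.80 to 0.90 when it favours the hypothesis, or to 0.66 when it opposes it.

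**The case against.** The strongest reply is that every step towards harm is hypothetical. The documents do not say who the examiner is, who uses the caliper, or who keeps the group count. Masking may be done in practice without being written down. This stands. A reader might infer that the examiner knows the group, or that the readings will be biased, and the documents support neither. They leave the question open, and open reading would comply with the plan as written.

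A second reply is that the effect is modest. At the plan's SD, shifts of 0.1 to 0.2 mm take the false-positive rate only to between 5.6% and 7.2%, and nothing in the documents supports a shift as large as 0.5 mm. This also stands, but only at an SD of 1.16 mm. That SD comes from an earlier study, and the Introduction calls the smooth-collar question undetermined. With a smaller SD, a smaller shift has the same effect.

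A third reply is that section IV lists bone level by visit, so change from V3 to V9 is an inference. That is correct, and it is treated above as an assumption. The general point does not need that particular interval: whichever change is compared, a group-dependent shift in it carries through.

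Finally, coded films would leave probing depth, the other primary measure, unprotected, and would not make non-randomised groups comparable. Both limits are real. Neither is a reason to leave the radiographic outcome unguarded.

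**Conclusion.** The point holds as a gap in design. The available text has no safeguard against a group-dependent reading of radiographic bone-level change by the single examiner, and the stated safeguards address repeatability only. It is more than missing detail, because a primary comparison between non-randomised groups could be read openly under the plan as it stands.

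The size is illustrative. With no true effect, 14 per group, change from V3 to V9 and an SD of 1.16 mm, the false-positive rate is 5.6% to 19.6% for assumed shifts of 0.1 to 0.5 mm. It doubles at about 0.30 mm, or at 0.20 mm or 0.13 mm under assumed SDs of 0.8 mm or 0.5 mm. A reader might take the upper figure as the trial's actual error rate. The documents do not support that, because they give no size for reader bias and do not show that any exists. This should be corrected, but it does not invalidate the design.

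**What to change.** Add a short paragraph to section III.C with these provisions:
- The periapical films read for marginal bone level are coded, with patient and group identifiers removed. The code keeps the films of one implant linked so that change can be calculated.
- The same calibrated examiner reads the coded films in random order, without access to the caliper values, the group list or the code.
- The readings are locked before thickness group is linked to them.

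The cost is a little image-coding work. The documents do not describe staffing, so who would do the coding is for the sponsor to settle. No extra reader, visit or patient procedure is needed, and the sample size and its power of 0.802 do not change.

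The fix reduces reader bias but may not remove it, since an examiner who has seen the patients may recognise some sites. It does not protect chairside probing depth, and it does not address confounding between the thickness groups.

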## D. Surgical protocol

Preliminary alginate impressions will be taken at the screening appointment for the purpose of making study models to then be able to fabricate a reference stent and surgical guide. On the

implant surgery visitvital signs will be taken. Local anesthesia will be performed by using local infiltration technique with 2% Lidocaine with 1:100k epinephrine or 1:50k epinephrine. Intrasulcular and crestal incision design will be made along the crest of the ridge, bisecting the existing zone of keratinized mucosa. Full-thickness flaps are raised on the buccal and lingual/palatal side up to or slightly beyond the level of the mucogingival junction, exposing the alveolar ridge of the implant surgical sites. Once the flaps are reflected and the bone is prepared, a surgical guide will be inserted and a series of drills are used to prepare the osteotomy site incrementally. All implants will be placed according to the manufacturer's protocol (Biohorizons Tapered Internal Implant, Laser-Lok, RBT) and the rough-smooth junction will be placed to the bone crest. The buccal mucosal thickness will be measured at different levels. Implants with 9-13 mm length and 3-5 mm width will be used. After implant placement a healing abutment will be connected and interrupted sutures will be placed to close the flaps. After suturing, standardized radiographs will be obtained. Other radiographs will be taken during the surgery to check implant angulation, these will not be standardized. The surgery is being done as part of standard of care. Subjects will be instructed to rinse with warm salt water once a day every day for two weeks. All subjects will be prescribed 500mg of amoxicillin to take 3 times a day for ten days. If the subject is allergic to Amoxicillin, they will be prescribed 250 mg of Zithromax 6 tablets total /sig. 2 tablets the 1st day and Q.D. (1 x per day) until gone. In addition, the subject will be prescribed 600 mg of ibuprofen, taken as needed, for pain control. The sutures will be removed in 2 weeks.

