## Statistical analysis

One way ANOVA will be used to detect any differences in between groups and student t test analysis will be conducted to assess mean differences between the groups.

-

†nQuery Advisor®, version 7.0., Los Angeles; Statistical Solutions Inc., 2007

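### Identical implant placement in the two non-randomized thickness groups is assumed but neither checked nor allowed for in the analysis, although the post-suture film can show it

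*Combined protocol and SAP*

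**What the plan says.** **Groups.** Section III.A forms two groups of 14 by mucosa thickness, with a cut at 2 mm. Assignment is by anatomy, not by randomization.

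**When thickness is measured.** Section III.B states: "A tension-free caliper will be used to measure mucosa thickness at the time of surgery". The table in section IV places it at the same visit ("Baseline (V3) Mucosa thickness"). The Surgical protocol (III.D) adds "The buccal mucosal thickness will be measured at different levels", a sentence that comes after the one on placement. The order of measuring and seating is not stated.

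**Placement.** III.D gives one target for all implants in both groups: "the rough-smooth junction will be placed to the bone crest". It states no tolerance, no recording of the achieved position as a variable, and no masking of the surgeon to thickness.

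**Films.** III.D continues: "After suturing, standardized radiographs will be obtained". Section IV lists marginal bone level at these times: "At screening (V1), implant/surgery baseline (V3), crown impression (V6), crown delivery (V7), 6m (V8), and 12m (V9) after crown placement". No section says which film is the starting point for marginal bone loss, or which point on the implant the level is measured from.

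**Analysis.** The Statistical analysis section reads: "One way ANOVA will be used to detect any differences in between groups and student t test analysis will be conducted to assess mean differences". It names no covariate and no check of placement.

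**The concern.** In a non-randomized comparison, the groups can differ in things other than the factor of interest. Here the treatment is meant to be the same in both groups, and the attribution of any difference to mucosa thickness depends on that. If the achieved junction-to-crest position differed on average between thin and thick sites, and position affects later bone change, the unadjusted difference would mix the two effects. Depending on direction, this could imitate a thickness effect or hide one.

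The operating team handles the tissue before the osteotomy, because the flaps are raised first, so thin tissue may be apparent before the implant is seated. That makes a difference in placement possible; it does not make it likely. As written, a reader of the results could not tell whether both groups received the same placement, even though a film that bears on the question is already scheduled.

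**Working it through.** **Inputs from the documents (Sample size section).** Two-sided α = 0.05, power 80%, means 1.450 and 0.170 mm, difference 1.280 mm, common SD 1.160 mm, 14 per group.

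**Step 1. Reproduce the planned size.** Standard error (SE) of the difference = 1.16 × √(2/14) = 0.438 mm. Noncentrality = 1.28 / 0.438 = 2.92 on 26 degrees of freedom. The exact two-sample t test has power 0.802 at 14 per group and 0.770 at 13, so the stated 14 reproduces. There is almost no spare power.

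**Step 2. Size of a possible bias.** Bias = (difference in mean depth) × (bone change per mm of depth). The documents give neither factor, so both ranges are assumptions: 0.2 to 0.4 mm for depth and 0.5 to 1.0 mm per mm for the slope.

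- Low end: 0.2 × 0.5 = 0.10 mm; 0.10 / 1.28 = 8% of the planned difference.
- High end: 0.4 × 1.0 = 0.40 mm; 0.40 / 1.28 = 31%.
- If every junction is exactly at the crest, the bias is zero.

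**Step 3. Effect on the unadjusted test** (noncentral t, 14 per group, SD 1.16 mm). The third column assumes no true thickness effect. The last assumes a true difference of 1.28 mm with the bias working against it.

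| Bias (mm) | Share of 1.28 mm | Rejection rate, no true effect | Power if bias opposes the effect |
|---|---|---|---|
| 0 | 0% | 5.0% | 80% |
| 0.10 | 8% | 5.6% | 74% |
| 0.25 | 20% | 8.5% | 62% |
| 0.40 | 31% | 14.2% | 49% |
| 0.50 | 39% | 19.6% | 40% |

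The 0.50 mm row lies outside the assumed range and shows where the problem would become serious.

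**Step 4. Price of adjusting for V3 distance.** Residual SD = 1.16 × √(1 − r²), where r is the within-group correlation of depth with bone loss (assumed), on 25 degrees of freedom. If the groups differ by D standard deviations in depth, the variance of the group estimate is multiplied by 1 + D²/4. For D = 1 that is 1.25.

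| r | Power, depth balanced | Power, groups 1 SD apart |
|---|---|---|
| 0 | 0.801 | 0.709 |
| 0.3 | 0.837 | 0.749 |
| 0.5 | 0.900 | 0.826 |

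**Step 5. Shared reading error.** If bone loss is V9 minus V3 and the covariate is the V3 reading, the V3 reading error enters both, with opposite sign in the change. With no biological relation, the fitted slope is −σ²(error) / [σ²(depth) + σ²(error)]. It is −0.5 if the two SDs are equal and −1/(9 + 1) = −0.1 if the error SD is one third of the depth SD. The adjusted group estimate then moves by that fraction of the observed depth imbalance. For a 0.4 mm imbalance this is 0.5 × 0.4 = 0.20 mm or 0.1 × 0.4 = 0.04 mm. The artefact is small only if the films are read precisely relative to the spread of depth.

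**The case against.** The strongest reply is that III.D already sets one crest-level target for both groups, with a surgical guide and the manufacturer's procedure. The concern needs departures from that rule, and the documents show none. This stands, and it limits the point to an unchecked assumption.

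Three stronger readings are tempting, and the documents do not support them:

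- **That measuring thickness at surgery makes depth differ by group.** It does not follow. Thin tissue would be visible whenever it was measured, and an earlier measurement would tell the surgeon more. The order within the operation is also not stated.
- **That the plan's own rationale gives a reason to seat implants deeper under thin mucosa.** The Introduction says bone may resorb when the soft-tissue dimension is insufficient. It says nothing about seating depth or junction position.
- **That the primary test should be replaced by an adjusted one.** If thin tissue did lead to deeper seating, depth would follow from the group, and adjusting for it would change the question from the overall effect of thickness to the effect at a fixed depth. Precision also falls when depth is imbalanced (step 4), and reading error is shared (step 5). Jaw, tooth site and implant dimensions vary too, and the documents do not single out depth as the one factor that must be in the primary model.

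It can also be said that the plan does not ignore starting position, because V3 is labelled baseline and loss computed from V3 subtracts the starting level. This is partly right. The plan does not say that V3 is the reference, and a change score removes the starting level without removing any effect of depth on later remodelling.

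Finally, even the largest assumed bias, 0.40 mm, is below one SE (0.44 mm). That is correct, and the low end of the range is minor. The high end would still nearly triple the false-positive rate.

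**Conclusion.** The point holds in a limited form. The contrast is not randomized, its interpretation relies on the same placement in both groups, and the planned analysis neither reports the achieved position by group nor examines its influence.

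The documents do not show that depth differs by group, and a reader should not infer it. The 0.10 to 0.40 mm bias, with null rejection of 5.6% to 14.2%, rests wholly on assumed depth differences and slopes, and it is zero if the target is met everywhere. Below about 0.25 mm of bias the consequence is slight for false positives, though power would already fall to 62% at 0.25 mm in the masking direction.

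This justifies a check and a sensitivity analysis. It does not justify a new primary analysis.

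**What to change.** In the Statistical analysis section:

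1. Define marginal bone loss as the change from V3 to V9, and name the rough-smooth junction as the reference point for reading.
2. Tabulate the V3 junction-to-crest distance, as the mean of mesial and distal readings on the standardized post-suture film, by thickness group.
3. Keep the unadjusted t test on bone loss as the primary result.
4. Add one prespecified sensitivity model: bone loss on thickness group plus V3 distance, with no further covariates given 28 patients. State in advance what difference between the two estimates counts as material, and qualify conclusions about thickness if it is reached.

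**Cost.** No extra visit or film is needed. The V3 film is already planned, and the added work is reading the distance from it. The sensitivity model uses one degree of freedom of 26. If depth is balanced and unrelated to loss, its power is 0.801 against 0.802 unadjusted. It is less precise if depth is imbalanced (0.709 at 1 SD and r = 0), and it carries the shared reading-error artefact, so both should be stated beside the result. No change to the placement rule is proposed.
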